Research plan

Study name

Study on the Identification of New Subtypes of Liver Cancer Based on 29 Genes and the Correlation with the Efficacy of Immunotherapy

Research Unit

Sir Run Run Shaw Hospital, Zhejiang University School of Medicine

Research Department

Department of General Surgery

Principal Investigator

[name]

Protocol Version Number

V1.0

Protocol Version Date

July 13, 2025

Study on the Identification of New Subtypes of Liver Cancer Based on 29 Genes and the Correlation with the Efficacy of Immunotherapy

I. Research Background

Liver cancer is one of the leading causes of cancer - related deaths worldwide. Its significant heterogeneity makes it difficult for traditional diagnosis and treatment models to meet the needs of individualized precision treatment. The application of immune checkpoint inhibitors (ICI) has brought breakthrough progress to liver cancer treatment, but there are still severe challenges in clinical practice. Although the dual - drug combination immunotherapy regimen has been widely used clinically, about 60% of patients will still experience primary or secondary drug resistance, resulting in significant differences in patients' treatment benefits.

There are two key bottlenecks in the current field that urgently need to be broken through, as follows:

(1) Lack of precise typing tools: The existing clinical and molecular typing systems cannot stably distinguish subtypes sensitive to immunotherapy, and it is difficult to provide reliable references for clinical decision - making, making it difficult to achieve precise application of immunotherapy;

(2) Lag in clinical translation process: Although a variety of immune checkpoint inhibitors have been clinically promoted and used, differentiated treatment strategies for different subtypes have not been established, and there is a lack of typing - guiding schemes verified by multiple centers.

To solve the above problems, this study intends to systematically develop a liver cancer typing system based on gene sets. The specific process is as follows: First, collect tumor and adjacent non - tumor tissue samples from patients with hepatocellular carcinoma, and perform whole - transcriptome sequencing to obtain transcriptome data; calculate the gene expression level of each patient sample based on the sequencing results, and then divide hepatocellular carcinoma into several subtypes through cluster analysis; map

these subtypes to the TCGA HCC cluster respectively, and screen out the subtypes that cannot be completely matched as new subtypes; further analyze the differential genes between the new subtypes and other subtypes. The screening criteria are: the ratio of gene expression between the new subtype and other subtypes > 4 , the false discovery rate (FDR) < 0.01 , and the gene expression in the new subtype > 1 and < 1 in other subtypes. Through this method, this study finally obtained a set of differential genes containing 29 genes.

Based on this, this study plans to use this 29 - gene set as a standard, obtain frozen surgical tissues from liver cancer patients for transcriptome sequencing, type the patients, and compare the differences in immunotherapy response between the new subtype and other subtypes at the large - sample level, aiming to provide a basis for precise immunotherapy of liver cancer.

II. Research Objectives

Evaluate the differences in immunotherapy response (including indicators such as objective response rate, disease control rate, and progression - free survival) between the new subtype defined by the 29 - gene set system and other subtypes, and confirm that patients with the new subtype have a higher response rate to immunotherapy.

III. Research Design and Methods

3.1 Research Objects

This study intends to include patients diagnosed with primary hepatocellular carcinoma who are treated in multiple centers including Sir Run Run Shaw Hospital, Zhejiang University School of Medicine (the leading unit). The relevant inclusion and exclusion criteria are as follows.

3.1.1 Inclusion Criteria

- ① ≥ 18 years old.
- ② Patients who are treated in multiple centers including Sir Run Run Shaw Hospital, Zhejiang University School of Medicine (the leading unit) and diagnosed with primary hepatocellular carcinoma by surgical pathological histology.
- ③ They have received targeted drug combined with immune checkpoint inhibitor treatment after the specimen collection time point (post - surgery or post - puncture) (that is: local treatments such as TACE, ablation, etc. are allowed before the start of targeted - immunotherapy combination treatment, but an interval of ≥ 4 weeks from the targeted - immunotherapy treatment is required).
- ④ Have measurable tumor lesions at the observation start point (according to RECIST 1.1 criteria), and can judge the tumor response status (including complete response CR, partial response PR, stable disease SD, or progressive disease PD) through imaging examination during the observation (such as post - treatment evaluation).
- ⑤ Have accessible frozen tumor tissue samples from surgical resection (sample volume $\geq 3g$); or tumor tissue samples obtained by puncture (puncture samples need to meet the pathological diagnosis requirements, and the sample quality can support subsequent transcriptome sequencing and analysis).
- ⑥ Voluntarily participate in this study and sign the informed consent form. If the subject

is unable to read and sign the informed consent form due to incapacity and other reasons, their guardian shall act as the agent for the informed process and sign the informed consent form. If the subject is unable to read the informed consent form (such as illiterate subjects), a witness shall witness the informed process and sign the informed consent form.

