3.2.2 Immunotherapy Response Evaluation System

3.2.2.1 Primary Observation Indicators

(1) Time to Progression (TTP)

Definition: The time from the start of targeted - immunotherapy combination treatment to

the first time meeting the mRECIST progression criteria.

Evaluation Criteria:

Target lesions: The sum of the diameters of arterial - phase enhancement increases by $\geq 20\%$ compared to the baseline and the absolute value $\geq 5\text{mm}$;

Non - target lesions: New lesions appear or existing non - target lesions have definite progression;

Distant metastasis: New occurrences of lung, bone, or lymph node metastases.

(2) Objective Response Rate (ORR)

Definition: The proportion of patients achieving complete response (CR, disappearance of arterial - phase enhancement in all target lesions) and partial response (PR, the sum of the diameters of target lesions is reduced by $\geq 30\%$).

Evaluation Time: For each line of targeted - immunotherapy combination treatment regimen received by the patient, the determination is made simultaneously at Week 8, Week 16, Week 24 of the regimen treatment, and at disease progression (or regimen termination). If the patient changes the targeted - immunotherapy treatment regimen due to poor efficacy, the treatment cycle of the new regimen needs to be recorded separately (Weeks 8, 16, 24 are recalculated from the start time of the new regimen), and the CR/PR status is evaluated at the corresponding time points. In the final ORR calculation, the CR/PR status achieved by the patient in a certain regimen only corresponds to the treatment cycle and evaluation time of that regimen, that is, it is clearly associated with the efficacy data of the specific targeted - immunotherapy combination regimen (including the first regimen or the subsequent new regimens).

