3.2.2.2 Secondary Observation Indicators

(1) Core Indicators of Immunotherapy Response

① Progression - Free Survival (PFS)

Definition: The time from the start of targeted - immunotherapy combination treatment to the first disease progression (determined according to mRECIST) or death from any cause, whichever occurs first.

Evaluation Method: Combine imaging examinations (once every 8 weeks) and survival status follow - up, and use the Kaplan - Meier method to perform Log - rank test to compare the differences between groups.

② Overall Survival (OS)

Definition: The time from the start of targeted - immunotherapy combination treatment to the patient's death from any cause; for lost - to - follow - up patients, the last follow - up date is used as the censored data.

Evaluation Method: Record the survival status through regular telephone/outpatient follow - up, draw survival curves, and analyze the differences between groups.

Dynamic changes of tumor markers.

(2) Dynamic Monitoring Related to Tumors

Dynamic changes of tumor markers

Monitoring Indicators: Alpha - fetoprotein (AFP), protein induced by vitamin K absence or antagonist - II (PIVKA - II), detected once at baseline and every 4 weeks.

Judgment Criteria: An increase of $\geq 20\%$ compared to the baseline and lasting for more than 4 weeks, combined with imaging results to assist in predicting the progression

risk (such as the early warning value of marker increase before imaging progression).

(3) Evaluation of Treatment - Related Status

① Correlation with Liver Function Status

Evaluation Nodes: Collect liver function data (Child - Pugh class, total bilirubin, albumin, INR) simultaneously when disease progresses.

Analysis Logic: Compare with baseline liver function, exclude interfering factors such as drug - induced liver injury, and evaluate the direct impact of tumor progression on liver function injury.

② Survival Analysis after Progression

Record Content: Treatment adjustment plans after disease progression (changing targeted drugs, adding local treatments, etc.).

Analysis Indicators: Post - progression survival (PPS, the time from disease progression to death or the end of the study), and analyze the impact on survival by combining differences in treatment plans.

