3.2.4 Protection Measures for Vulnerable Groups

The vulnerable groups that may be involved in this study include the mentally ill/cognitively impaired/critically ill patients/elderly/illiterate, etc. This study will take the following measures to protect their interests: 1) Ensure that the subjects are fully informed. If the subject is unable to read and sign the informed consent form due to

incapacity, their guardian shall act as the agent for the informed process and sign the informed consent form. If the subject is unable to read the informed consent form (such as illiterate subjects), a witness shall witness the informed process and sign the informed consent form. 2) If it is a critically ill patient, the researcher will closely monitor the vital signs of such subjects, and report in a timely manner once there is a situation.

IV. Sample Size Calculation

This study plans to include subjects from 10 top - three hospitals nationwide. Calculate the new typing score of HCC for each sample through the 29 - gene signature. It is estimated that there will be 100 cases in the new typing cohort and 250 cases in other typing cohorts.

Therefore, the final planned total sample size of this study is 350 cases.

V. Data Management and Confidentiality

All records related to the subject's identity will be kept confidential, and these materials will not be disclosed outside the scope permitted by relevant laws and/or regulations.

VI. Informed Consent

For the prospective observational study part involved in this study, before the subjects are included in this study, the researcher responsible for the informed consent discussion should introduce the purpose, nature, procedure, and possible benefits and risks of this study to them in written form completely and comprehensively. The subjects should be informed that they have the right to withdraw from the study at any time. Before inclusion, each subject should be fully informed and have sufficient time to consider whether to participate. Only after the subject voluntarily participates and signs the informed consent form can they be included in this study.

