For the retrospective study part involved in this study, if it only involves the use of previously saved clinical data and biological specimens, does not interfere with the clinical diagnosis and treatment process, and will not have an adverse impact on the health of the subjects. During statistical analysis, the identity of the subjects is represented by codes, and there is no disclosure of the subjects' privacy and personal information. This part of the study does not involve commercial interests and can apply for exemption from informed consent.

VII. Adverse Events and Related Handling Measures

For the prospective observational study part involved in this study, only clinical data of the subjects are collected, no additional biological samples are collected, and the clinical diagnosis and treatment process is not interfered with, which will not have an adverse impact on the health of the subjects.

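### Inclusion criterion 6 demands a signed consent form without exception, but Section VI lets the retrospective part seek exemption; applied literally, the criterion selects survivors while survival is counted from treatment start

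*Protocol*

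**What the plan says.** - **Protocol 3.1.1, criterion 6:** the patient must "Voluntarily participate in this study and sign the informed consent form". For a subject unable to read and sign, "their guardian shall act as the agent for the informed process and sign the informed consent form"; a witness signs for those who cannot read. Nothing is said about retrospective or deceased patients.
- **Protocol 3.1.1, criterion 3:** "They have received targeted drug combined with immune checkpoint inhibitor treatment after the specimen collection time point".
- **Protocol 3.1.1, criterion 4:** imaging during observation must be such that one "can judge the tumor response status".
- **Protocol VI, prospective part:** "Only after the subject voluntarily participates and signs the informed consent form can they be included in this study".
- **Protocol VI, retrospective part:** where only stored data and specimens are used, this part "can apply for exemption from informed consent".
- **Protocol 3.2.2.1 and 3.2.2.2:** TTP (primary), PFS and OS (secondary) share one time origin. PFS, for example, is "The time from the start of targeted - immunotherapy combination treatment to the first disease progression" or death.
- **Protocol 3.2.2.2 and 3.2.3.2:** the methods are Kaplan-Meier, log-rank and Cox.
- **Protocol IV:** 350 patients from 10 hospitals, 100 of the new subtype and 250 others. The split between retrospective and prospective patients is not given.

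**The concern.** Eligibility and the consent section give different rules for the same patients. A hospital working from 3.1.1 would turn away a retrospective patient who had died, because nobody can sign. A hospital working from Section VI, with an exemption in hand, would admit that patient. Under the first rule, entry depends on having lived from treatment start to signature, yet that interval is still counted as survival.

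At stake are the OS and PFS curves and medians, and to a smaller degree TTP and ORR. If hospitals resolve the conflict differently, selection also varies by site. A later analysis plan could adjust the risk set, but it could not bring back patients whom the eligibility rule kept out, so the protocol is the place to settle this.

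**Working it through.** **1. The passages side by side.** Criterion 6 applies to all subjects. The signature rule in Section VI opens with a restriction to the prospective part, and the retrospective paragraph allows an application for exemption without saying that it has been granted. A deceased retrospective patient fails criterion 6 and may be eligible under Section VI. Both cannot hold.

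**2. Figures in the plan.** The only design figure is 100 + 250 = 350, which adds up. It has no bearing on this point. The protocol states no consent lag, no median survival and no retrospective share, so what follows is illustration.

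**3. Assumptions.** ORR 30%. Exponential survival with base hazard ln2/18 per month; responders at 0.6 times and non-responders at 1.2 times that hazard. Lag from treatment start to consent uniform on 0 to A months, applied to **all** patients. Entry only if alive at consent.

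**4. True values.**
- S(12) = 0.3 × 2^(-0.4) + 0.7 × 2^(-0.8) = 0.3 × 0.758 + 0.7 × 0.574 = 0.629.
- Median OS = 18.1 months.

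**5. Share kept.** For hazard λ, the share alive at consent is (1 − e^(−λA))/(λA). For A = 12:
- responders: λA = 0.4 ln2, kept 0.873;
- non-responders: λA = 0.8 ln2, kept 0.768;
- overall: 0.3 × 0.873 + 0.7 × 0.768 = 0.799, so 20% are excluded;
- apparent ORR: 0.3 × 0.873 / 0.799 = 32.8%;
- apparent 12-month OS: 0.629 / 0.799 = 78.7%. With A no greater than 12, everyone alive at 12 months has been kept.

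| Lag (months) | Excluded | ORR | 12-month OS | Median OS (months) |
|---|---|---|---|---|
| none | 0% | 30% | 63% | 18.1 |
| 0-3 | 6% | 31% | 67% | 19.7 |
| 0-6 | 11% | 31% | 71% | 21.3 |
| 0-12 | 20% | 33% | 79% | 24.2 |

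If only a fraction of patients is subject to the literal rule, the distortion is smaller.

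**6. The subtype comparison.** A separate simulation took a true hazard ratio of 0.6 for the new subtype, reference median OS of 12, 18 or 24 months, and the same lag distribution in both groups (0-6, 0-12 or 0-24 months). The Cox hazard ratio without delayed entry stayed within about 0.03 of the ratio with it; the largest gap was 0.581 against 0.607. The new subtype's share of the sample rose from 100/350 = 28.6% to between 29% and 33%. With **unequal** lags the picture changes: with no true difference, a 0-12 month lag in one group and none in the other, and follow-up capped at 36 months, the crude death-rate ratio is 0.76. That is an extreme case.

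**7. Delayed entry for TTP and PFS.** Consent requires being alive, not progression-free. With a 0-12 month lag and an assumed exponential median TTP of 6 months, λA = 2 ln2 = 1.386, and the share progressed before consent is 1 − (1 − 0.25)/1.386 = 46%. With a median of 10 months it is 32%. Entry at consent would discard all of these patients and their events.

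**The case against.** A reader might infer that nobody can enter without signing, so that every early death is lost. The protocol does not support that. Section VI confines signed consent to the prospective part, and patients who died before enrolment would naturally fall in the retrospective part, where an exemption can be sought. That the text speaks of applying is ordinary, since investigators cannot grant their own waiver. This stands, and it reduces the point to a conflict between two sections with a conditional consequence.

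A reader might also infer from criterion 3 that every consenting patient signs after treatment start. The criterion orders specimen and treatment and sets the interval from local therapy; it fixes no consent date. Other text, such as a marker measurement at baseline, fits enrolment at or before treatment start. Prospective patients who sign by then carry no such bias.

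The lags are assumptions, and applying them to all patients is close to a worst case. The study's aim is a comparison, and the hazard ratio hardly moves under equal lags. Both stand. Handling of late entry can also be left to an analysis plan that is not shown, so its absence here is not the fault.

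What does not fall away is that criterion 6 is unconditional. The guardian provision does not repair it: it is written for a subject who cannot read and sign, and does not mention death.

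**Conclusion.** The contradiction between criterion 6 and Section VI is certain. The survivor selection is conditional: it follows if criterion 6 is applied as written to retrospective patients, at all hospitals or some, or if the exemption is not obtained. It also affects any prospective patient who happens to consent after treatment start.

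Its size cannot be stated from the protocol. The table gives a range under stated assumptions, not an expected effect. The damage falls on absolute survival figures more than on ORR. Bias in the subtype comparison is not shown; it would need the lag or the retrospective share to differ by subtype, on which the protocol is silent. The point is worth correcting before enrolment because the edit costs almost nothing and excluded patients cannot be recovered at analysis.

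Criterion 4 is a separate matter: requiring a judgeable response can also remove early deaths, and the consent edit does not change that.

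**What to change.** 1. In 3.1.1, limit criterion 6 to the prospective part and refer to Section VI for the rest.
2. In Section VI, state that the retrospective part enters all consecutive patients who meet the other criteria, deceased included, under the exemption.
3. Record the consent date and whether each patient is retrospective or prospective.
4. For any patient who consents after treatment start, enter the OS risk set at the consent date. Do not do this for TTP or PFS, where it would drop those who progressed before consent. Delayed entry does nothing for ORR. For those three endpoints the eligibility edit is the remedy, and any remaining selection among late consenters should be acknowledged.

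The cost is two sentences in the protocol, two data fields and a start-stop term in the OS analysis. The downside is small: some OS person-time before consent is dropped.

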3.1.2 Exclusion Criteria

① Received any local treatment during the targeted - immunotherapy combination treatment (including during treatment and within 4 weeks after treatment interruption), including:

Transcatheter arterial chemoembolization (TACE), transcatheter arterial embolization (TAE), drug - eluting bead transcatheter arterial chemoembolization (DEB - TACE) and other vascular interventional therapies;

Radiofrequency ablation, microwave ablation, cryoablation, laser ablation and other ablation therapies;

Stereotactic body radiation therapy (SBRT), three - dimensional conformal radiation therapy, intensity - modulated radiation therapy and other local radiation therapies;

Intratumoral injection therapy, high - intensity focused ultrasound (HIFU) and other local physical/chemical therapies.

② Local treatment was initiated before the start of targeted - immunotherapy combination treatment, and the local treatment continued into the targeted - immunotherapy treatment period (that is, there was an overlap between local treatment and targeted - immunotherapy treatment or the interval was < 4 weeks).

③ Complicated with other active malignant tumors (except for those with cured basal cell carcinoma of the skin, carcinoma in situ of the cervix, and papillary thyroid carcinoma with no recurrence for more than 5 years after surgery).

④ Severe impairment of important organ functions:

Liver function: Child - Pugh class C, or total bilirubin > 3 × ULN;

Renal function: Serum creatinine > 1.5 × ULN and estimated glomerular filtration rate (eGFR) < 50 ml/min;

Cardiac function: New York Heart Association (NYHA) cardiac function class III - IV, or left ventricular ejection fraction (LVEF) < 50%.

⑤ Have uncontrolled active infections, including:

Hepatitis B virus DNA > 2000 IU/ml (without receiving antiviral treatment);

Hepatitis C virus RNA positive and without receiving antiviral treatment;

Active tuberculosis infection, septicemia, etc.

⑥ Have a history of autoimmune diseases and currently still need to use systemic glucocorticoids (prednisone > 10 mg/day) or other immunosuppressive therapies.

⑦ Pregnant or lactating women, or patients planning to become pregnant during the study.

⑧ Have a definite history of allergy to the targeted drugs or immune checkpoint inhibitors involved in the study.

⑨ The researcher believes that there are other factors that may affect the judgment of treatment response (such as uncontrolled hypertension, coagulation dysfunction, simultaneous use of other antineoplastic drugs during targeted - immunotherapy

treatment, etc.).

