3.1.3 Withdrawal Criteria

- ① The subject voluntarily requests to withdraw from the study and signs a written withdrawal statement.
- ② Severe adverse events occur during the study (such as grade 3 or above immune - related adverse reactions, severe infections, etc.), and after the researcher's evaluation, it is considered that continued participation in the study may endanger the subject's safety.
- ③ The subject does not comply with the research protocol, including but not limited to: failure to follow up at the specified time, refusal to complete necessary examinations, unauthorized acceptance of other antineoplastic treatments, etc.
- ④ It is found during the study that the subject does not meet the inclusion criteria of this study (such as the previous treatment history does not meet the requirements found in the baseline data verification).
- ⑤ The subject is unable to continue participating in the study due to disease progression, death, and other reasons.
- ⑥ The study is terminated in advance (such as protocol revision, ethical committee requiring termination, etc.).

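### Exclusion ① selects patients on local treatment given after time zero for TTP, PFS and OS; in the retrospective part those patients never enter the data

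*Protocol*

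**What the plan says.** The first primary indicator, TTP (Protocol section 3.2.2.1), is defined as "The time from the start of targeted - immunotherapy combination treatment to" progression by mRECIST. PFS and OS (section 3.2.2.2) use the same starting point.

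Exclusion ① (section 3.1.2) reads "Received any local treatment during the targeted - immunotherapy combination treatment (including during treatment and within 4 weeks after treatment interruption", and then lists vascular, ablative, radiation and other local procedures. Local treatment before the combination is covered separately, by inclusion ③ and exclusion ②. Exclusion ⑨ leaves to the researcher's judgement other factors that may affect the assessment of response. One of its examples is "simultaneous use of other antineoplastic drugs during targeted - immunotherapy" treatment.

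Inclusion ④ (section 3.1.1) requires a measurable lesion at the start. It also requires that response can be judged as CR, PR, "stable disease SD, or progressive disease PD) through imaging examination during the observation (such as post - treatment evaluation".

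Sections VI and VII describe two parts: a retrospective one using stored data and specimens, and a prospective observational one with consent before inclusion. Among the withdrawal reasons in section 3.1.3, ③ covers taking other anticancer treatment without authorisation, and ⑤ reads "The subject is unable to continue participating in the study due to disease progression, death, and other reasons".

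Section 3.2.2.2 asks for a record of "Treatment adjustment plans after disease progression (changing targeted drugs, adding local treatments, etc", to be analysed together with post-progression survival.

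**The concern.** Eligibility for a cohort followed from treatment start should depend only on what is known at treatment start. Exclusion ① depends on the later course. Its window opens when the combination begins and closes 4 weeks after its interruption, so it lies wholly after time zero.

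Local treatment in that window is unlikely to be unrelated to outcome. It may be added because the tumour progressed, or because it shrank enough to be treated locally. Dropping those patients changes the mix of outcomes among those who remain.

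TTP and ORR are the primary indicators, and the objective is to confirm a higher response rate in the new subtype. Nothing in the protocol makes the losses equal across subtypes. If subtype does affect the course of disease, as the study supposes, unequal losses are plausible.

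**Working it through.** **When each criterion is known**

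| Criterion | Known at time zero? | Retrospective part | Prospective part |
|---|---|---|---|
| Exclusion ① | No | Course already on record; patient never enters the data | Patient already enrolled; ① with withdrawal ③ could remove them |
| Inclusion ④, second half | No, if read as actual assessability | Patient with no post-baseline scan can be left out | May mean expected assessability; removal only possible |
| Exclusion ⑨, other drugs | Depends on reading | As ①, or a regimen known at the start | As ①, or a regimen known at the start |

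Withdrawal ④ names only unmet inclusion criteria, so it does not carry exclusion ① forward after enrolment. Withdrawal ③ is the rule that could.

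**Inputs.** From the protocol: 100 and 250 patients (section IV), P < 0.05 (section 3.2.3.4, taken as two-sided), chi-square test (section 3.2.3.3), imaging every 8 weeks (section 3.2.2.2). The only sample-size figure to reproduce is 100 + 250 = 350. Every share, ORR and median below is an assumption, and 100 and 250 are taken as the numbers left after exclusion.

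**ORR within a group under exclusion ①.** Remove a fraction qn of non-responders and qr of responders from a group with true ORR p:

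observed ORR = p(1−qr) / [p(1−qr) + (1−p)(1−qn)]

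With p = 30%:
- qn = 10%: 0.30/(0.30 + 0.63) = 32.3%; qn = 20%: 0.30/(0.30 + 0.56) = 34.9%.
- qr = 10%: 0.27/(0.27 + 0.70) = 27.8%; qr = 20%: 0.24/(0.24 + 0.70) = 25.5%.

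**TTP within a group.** Assume an exponential TTP with median 6 months and 12 months of follow-up. Then P = 1 − 2^(−12/6) = 75% progress. If a share g of them is removed, the median among those kept solves (1 − S(t))(1 − g)/(1 − gP) = 0.5.
- g = 10%: 1 − S = 0.5 × 0.925/0.9 = 0.514, so t = 6.24 months.
- g = 20%: 1 − S = 0.5 × 0.85/0.8 = 0.531, so t = 6.56 months.

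**Subtype comparison, true ORR 30% in both.** Exact binomial enumeration of the uncorrected chi-square test gives a rejection rate of 5.0% with equal removal. Removing 10% (new) vs 20% (other) of non-responders gives 7.35%; reversed, 7.84%.

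**Subtype comparison, true ORR 40% vs 25%** (gap 15.0 points, power 79%, odds ratio 2.0, response ratio 1.60)

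| Removed, new vs other | Observed ORR | Gap | Power |
|---|---|---|---|
| Non-responders 10% vs 20% | 42.6% vs 29.4% | 13.1 | 65% |
| Non-responders 20% vs 10% | 45.5% vs 27.0% | 18.4 | 91% |
| Responders 10% vs 20% | 37.5% vs 21.1% | 16.4 | 88% |
| Responders 20% vs 10% | 34.8% vs 23.1% | 11.7 | 61% |
| Non-responders 20% vs 20% | 45.5% vs 29.4% | 16.0 | 81% |

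In the last row the odds ratio is still 2.0, but the response ratio falls to 1.55 and the gap widens.

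**Time-to-event comparison.** A simulation of PFS assumed exponential times, a median of 8 months in the other subtypes, 20% of events as deaths, censoring at 18 months and 400,000 patients per group. Removing 20% to 40% of progressors equally moved a true hazard ratio of 0.60 to 0.58–0.56 (estimated as an event-rate ratio). Unequal removal moved a true 1.00 to about 0.91 (30% new vs 10% other) or 1.09 (10% vs 30%).

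**Inclusion ④, retrospective part.** With exponential OS, the share dying before Week 8 (1.84 months) is 1 − 2^(−1.84/median): 10.1% at a median of 12 months and 5.2% at 24. If a quarter to a half of these had no earlier scan, the share left out is u = 1.3% to 5.0%. A 30% ORR then reads 0.30/(1 − u) = 30.4% to 31.6%. Contrasts between subtypes of 1.3% vs 2.5% or 2.6% vs 5.0%, in either order, give rejection rates of 5.1% to 5.4%.

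**The case against.** **The aim is sound.** Local treatment during the combination makes response hard to attribute to the drugs. That stands, but it argues for dating the treatment and pre-specifying its handling. Excluding the patient replaces confounding with selection on the course of disease.

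**The analysis plan could deal with it.** A reader might infer that the loss is irreversible throughout. The documents support that only where ① is applied to a completed treatment course. In the prospective part consent precedes inclusion, so a patient who later receives local treatment is already enrolled and can be retained.

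**Equal losses would cancel.** Only in part. An equal share u of unassessable non-responders leaves the response ratio unchanged, and equal removal of non-responders under ① leaves the odds ratio unchanged. Neither leaves the ORR difference unchanged, and neither reassurance extends to TTP.

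**Inclusion ④ is minor.** Agreed. Scanned early progressors stay in, because PD is an accepted outcome. Stopping before Week 8 does not by itself make a patient unassessable, because "the determination is made simultaneously at Week 8, Week 16, Week 24 of the regimen treatment, and at disease progression (or regimen termination". A reader might infer a denominator of evaluable patients only; the protocol states none.

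**Exclusion ⑨ may be a baseline condition.** That reading is open: the example stands beside conditions such as uncontrolled hypertension. It is weak support here.

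**Withdrawal ⑤ might seem to end follow-up at progression.** The text does not establish this. For OS the protocol says "Record the survival status through regular telephone/outpatient follow - up", and it plans a post-progression survival analysis. The wording only leaves open whether progression alone ends data collection.

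**Conclusion.** The point holds for exclusion ①, and as a small secondary matter for the second half of inclusion ④ in the retrospective part. That ① acts after time zero follows from the text. It also conflicts with the planned record and analysis of local treatment added after progression, wherever that treatment falls inside the window; the sections must be reconciled.

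Within a group, removing patients treated locally at progression lengthens TTP, while ORR can move either way. Between subtypes the bias can also run either way. A reader might infer that it works against the study's hypothesis if the new subtype loses fewer patients. In the 40% vs 25% illustration that is so when non-responders are lost (15.0 to 13.1 points), but the gap widens when responders are lost (to 16.4).

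All magnitudes rest on assumed shares, rates and medians. The documents supply none, so the actual size and direction are unknown. This should be fixed; confidence is moderate.

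**What to change.** - Word exclusion ①, and ⑨ where it concerns later drugs, by facts known at the start of the combination. Limit ④ to a measurable lesion at baseline.
- Include every otherwise eligible patient who started the combination, in both parts.
- Keep patients with later local or other antineoplastic treatment in the data, record its date, and name it an intercurrent event with pre-specified handling. The choice of strategy can be left to the SAP.
- Keep patients without a post-baseline scan in the ORR denominator and in the time-to-event analyses.
- Report the numbers locally treated and not assessable by subtype.
- Reconcile sections 3.1.2, 3.1.3 (withdrawal ③ and ⑤), 3.2.2.1 and 3.2.2.2, so that neither later treatment nor progression alone ends data collection.

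This concerns who is counted, not how patients are treated. The cost is amendment wording and the recording of treatment dates, mostly from records already being extracted. ORR will be slightly lower once unassessed patients count in the denominator, and response after local treatment will be harder to attribute.
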